Swiss TPH	Swiss Tropical and Public Health Institute
TIMCI	Tools for integrated management of childhood illness
ToC	Theory of Change
UCAD	Université Cheikh Anta Diop de Dakar
UoN	University of Nairobi
US FDA	United States Food and Drug Administration
VPN	Virtual Private Network
WHO	World Health Organisation

1 Summary

Background / rationale

Achieving global targets for child mortality reduction in low- and middle-income countries (LMICs) requires significant improvements in the detection and management of severely ill children. Existing guidelines are inconsistently implemented by healthcare providers and, as they are based on clinical signs, are inadequate for the detection of hypoxaemia, a strong predictor of mortality.

The overall goal of the Tools for the Management of Childhood Illness (TIMCI) project is to reduce morbidity and mortality in sick children attending primary care facilities, while supporting the rational and efficient use of diagnostics and medicines by healthcare providers. The evaluation component of the project seeks to generate evidence on the health impact, operational priorities, cost and modelled cost-effectiveness of introducing pulse oximetry, embedded into a Clinical Decision Support Algorithm (CDSA), at primary care level in LMICs, for children 0 – 59 months of age, to facilitate national and international decision-making on scale-up.

Study design

Health impact will be assessed through a quasi-experimental pre-post study, comparing clinical care of children attending primary care facilities in a pre-intervention period with those attending facilities following introduction of the intervention. The intervention package will be piloted and refined in parallel with the pre-intervention study period.

This will be complemented by embedded mixed methods sub-studies to evaluate key components of quality of care and gain a deeper understanding of the implementation processes, mechanisms and context following a realist approach. These studies include modified Service Provision Assessments (SPAs), a facility-based process mapping and time-flow study, qualitative studies with caregivers, healthcare providers and key stakeholders, a survey sent to selected key stakeholders, a desk-based project document and monitoring and evaluation (M&E) review, and a cost and modelled cost-effectiveness study.

Study setting

The study setting encompasses facility-based primary care level in Kenya (Kakamega, Kitui and Uasin Gishu), and Senegal (Thiès). Caregivers often attend different types of facilities to meet their primary care needs; the study setting therefore includes a diverse range of facilities providing primary care services, including outpatient settings within larger health centres in addition to the more traditionally-labelled primary care facilities. This includes Level 2 (dispensaries) and Level 3 (health-centres / sub-county hospitals) in Kenya, and health posts in Senegal.

Key Eligibility Criteria

Consenting government-designated healthcare facilities providing outpatient curative primary care services for children 0 – 59 months of age will be included. Facilities will be excluded if they use pulse oximetry as a routine part of outpatient consultations of children prior to the start of the intervention.

Children 0 – 59 months, for whom caregivers provide consent, will be eligible if attending any study facility with an illness, excluding those admitted as inpatients within the facility, or attending for a consultation related to trauma only.

Caregivers of enrolled children, and healthcare providers at study sites involved in the care of children 0 – 59 months of age, and stakeholders involved in or affected by the intervention, will be eligible for inclusion in the applicable studies.

Interventions

The TIMCI project will introduce pulse oximetry, incorporated into a CDSA, into primary care facilities, supported by targeted training and embedded into monitoring, supportive supervision and maintenance systems.

The pulse oximeters provided in the study will be UNICEF-approved handheld pulse oximeters with paediatric and neonatal probes. The criteria for pulse oximetry use, on which healthcare providers will be trained, are:

- ξ All children under 2 months of age
- ξ Children 2 – 59 months of age presenting with cough / difficulty breathing
- ξ Children 2 – 59 months of age with Integrated Management of Childhood Illness (IMCI) signs of moderate / severe disease (IMCI 'yellow' or 'red' classification)

Healthcare providers will be advised to use a cut-off of SpO₂ <90% for referral, unless specific national guidance states otherwise (for example in Senegal, where it is likely that a <92% SpO₂ cut-off may be instituted). Different SpO₂ cut-offs for referral for sites at high altitude will be finalised with the International Advisory Group (IAG) and Ministries of Health (MoHs).

The above guidance will be incorporated into a tablet-based CDSA, which guides healthcare providers through medical consultations with an algorithm called electronic point-of-care tool (ePoct+). The clinical algorithm will be adapted to reflect national guidelines for the management of children 0 – 59 months of age in primary care (based on IMCI and additional relevant case management guidelines), and will be validated through consultation of international and national experts in each country.

Outcomes

Two primary outcomes will be assessed between the pre-intervention and the last intervention period of the pre-poststudy:

- ξ Proportion of children referred by a primary care healthcare provider to a higher level of care (either to a hospital or to an inpatient part of a larger primary healthcare facility) at Day 0 consultation
- ξ Proportion of children prescribed an antibiotic at Day 0 primary care consultation

Important secondary outcomes include:

- ξ Proportion of children with a severe complication (death or secondary hospitalisation) by Day 7
- ξ Proportion of children admitted to hospital within 24 hours of the Day 0 primary care consultation and as a result of a referral (used as a proxy for 'appropriate referral')
- ξ Proportion of children who completed referral, as reported at Day 7 follow-up
- ξ Proportion of children cured (defined as caregiver reported recovery from illness) at Day 7 follow-up
- ξ Proportion of children with hypoxaemia (according to differing cut-offs) with severe complication

Sub-group analyses will include age (under 2 months, 2 – 12 months, 13 – 59 months), sex, and clinical presentation (with cough / difficulty breathing, fever, other). Exploratory interrupted time series analysis across the 5 quarters of the pre-post study will be conducted, along with other exploratory analyses of individual and health system factors associated with health and patient-centred outcomes.

Mixed methods sub-studies will mostly be exploratory, to evaluate quality of care outcomes and explore perceptions, values, attitudes and beliefs. Process evaluation criteria will be evaluated according to the Medical Research Council criteria.

Cost and modelled cost-effectiveness will assess:

- ξ Full implementation cost of the intervention per focal country (cost to health system as well as direct costs paid by the household to the health system)
- ξ Cost per child assessed using pulse oximetry devices and CDSA per country compared to without these supports.
- ξ Modelled cost per DALY averted attributed to the introduction of pulse oximetry and CDAs

Sample size

The sample size for the pre-post study is calculated separately for each country, based on comparison between pre- and post-intervention periods. In order to detect a difference in

referral from primary care from 3% to at least 4.5%, with 80% power, we initially estimated a sample size in each country as follows:

- ξ Kenya – 17 facilities, recruiting an average of 690 children per facility in each period, equating to 11,730 children per period
- ξ Senegal – 18 facilities, recruiting an average of 510 children per facility in each period, equating to 9,180 children per period

For the antibiotic prescription primary outcome, this would enable a minimum detectable reduction of 18% in both Kenya and Senegal.

Following lower than anticipated recruitment in the pre-intervention period, sample size calculation was revised. As a result, two additional facilities were added per country and the pre-intervention period was extended from an initially anticipated 3 months to a 6 – 8 month period. A decision was also taken to target a post-intervention sample size of at least the same as the pre-intervention sample size, as well as a minimum duration of 9 months post-intervention to allow for stabilisation over time and some seasonal overlap of pre- and post-intervention periods.

Service provision assessments and process mapping will be conducted in 8 – 10 study facilities per country, stratified by rural / urban location and facility type. At each facility at each time point, 10 – 30 children per facility will be included, resulting in an estimated sample size of 800 – 1000 clinical observations, time-flow observations and exit interviews per country over the study period.

Final sample size for qualitative studies will be determined by reaching thematic saturation. For those countries choosing to conduct qualitative data collection pre-intervention an estimated 10-20 IDIs with caregivers and health care providers and 10-20 KIIs with stakeholders will be conducted. Per country, an estimated total of 35-45 in-depth interviews (IDIs), 6 – 8 walking interviews and 6 focus group discussions (FGDs) will be conducted with caregivers, spread across the period of implementation. Similarly, 35 – 45 IDIs and 6 FGDs will be conducted with healthcare providers, and approximately 45 key informant interviews with stakeholders.

Ethics Review

Following independent scientific merit review, the protocol will be submitted to all relevant research ethics committees / institutional review boards in each country and the WHO ethical review committee.

Estimated study timeline

Pending all relevant ethical approvals, first enrolment is anticipated to be in Q2 2021, with completion of data collection in Q1 2023.

Depending on the evolution of the Covid-19 pandemic, we will keep implementation, research processes and timelines under review and inform the necessary bodies and institutions accordingly of any changes.

2 General information

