3.3 The TIMCI project

The Tools for Integrated Management of Childhood Illness (TIMCI) project builds on this hypothesis to form part of the response to the need for better mechanisms to detect and manage children with severe illness in LMICs. It is a 4 year UNITAID-funded project, focused on the interventions of pulse oximetry and CDSAs in primary care, organised into four main outputs: (1) introduction of pulse oximetry and CDSAs in four countries (India, Kenya, Senegal and Tanzania); (2) evidence generation for pulse oximetry and CDSA introduction; (3) market strengthening for adapted multi-modal devices; and (4) creating conditions for national and global scale-up and sustainable use of these tools.

This protocol focuses on the evidence generation component of the TIMCI project in Kenya and Senegal (a separate protocol has been developed for India and Tanzania to reflect a different study design).

To our knowledge, no large scale studies have systematically evaluated the health impact, cost and optimal implementation approaches of pulse oximetry, alone or embedded into a CDSA, for children with a broad range of clinical diagnoses in primary care.

4 Goal & objectives

The overall goal of the TIMCI project is to reduce morbidity and mortality in sick children attending primary care facilities, while supporting the rational and efficient use of diagnostics and medicines by healthcare providers. The evaluation component of the project in Kenya and Senegal seeks to generate evidence on the health impact, operational priorities, cost and modelled cost-effectiveness of introducing pulse oximetry, embedded into a CDSA, into primary care in LMICs, for children 0 – 59 months of age, to facilitate national and international decision-making on scale-up. Specific objectives, according to these themes, include:

Health and quality of care impact

To evaluate the impact on health and quality of care outcomes of sick children 0 – 59 months of age of introducing pulse oximetry, embedded into a CDSA, for facility-based primary care, compared to routine care, including on:

- ξ Referral and hospitalisations
- ξ Antimicrobial prescription
- ξ Adherence by primary healthcare providers to key components guidelines

To assess the prevalence of severe, moderate and mild hypoxaemia among sick children attending primary care, and understand the association of different degrees of hypoxaemia with adverse outcomes, according to socio-demographic and clinical features.

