Lastly, children presenting with signs of moderate or severe disease are included to ensure detection of children with illnesses such as sepsis, meningitis, malaria, malnutrition, diarrhoea, anaemia that may also present with hypoxaemia.^{16,17} Children with mild disease – such as diarrhoea with no evidence of dehydration, fever with no evidence of malaria, meningitis / encephalitis, or complicated measles – are very unlikely to have hypoxaemia and pulse oximetry use will therefore not be advised in this group.

In certain circumstances, there may be a deviation from these criteria for operational reasons. Such circumstances will be agreed with local decision-makers, but, for example, may include the use of pulse oximetry during a triage step in large, high volume facilities. In such circumstances, preference may be given to using pulse oximetry on all sick children. In the event that this occurs, children found to have low oxygen saturation will be triaged for immediate assessment by a clinician, who may repeat the pulse oximetry measurement if needed.

In Kenya, the Ministry of Health opted to recommend pulse oximetry be used in the assessment of all sick children under five years of age.

Healthcare providers will be advised to use a cut-off of SpO₂ <90% for referral in Kenya, and SpO₂ <92% in Senegal in line with national guidance.⁴⁷ The message to refer children with other signs will be reinforced. Different SpO₂ cut-offs for referral for sites at high altitude will be finalised with the IAG and MoHs, given that the normal range for SpO₂ varies with altitude, but this is unlikely to affect cut-offs below 2500m.⁴⁸

Healthcare providers will be advised to only take one measurement for children with severe or moderate disease and will be advised not to attempt to obtain a reading for more than 5 minutes (most readings are obtainable within this time)^{13,49,50}. However, if a child with no other sign of moderate or severe disease (i.e. IMCI 'green' category) is found to have SpO₂ <90% (or altitude-specific cut-off), healthcare providers will be advised to repeat the reading. In cases of conflicting readings (i.e. one <90% and one ≥90%, or altitude-specific cut-off), a third reading will be advised as confirmatory.

The above guidance will be incorporated into the CDSA, described in detail below.

Clinical Decision Support Algorithm

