6.4 Outcomes

6.4.1 Quasi-experimental pre-post study

Two primary outcomes will be assessed between the pre-intervention and post- intervention period:

- ξ Proportion of children referred by a primary care healthcare provider to a higher level of care (either to a hospital or to an inpatient part of a larger primary healthcare facility) at Day 0 consultation
- ξ Proportion of children prescribed an antibiotic at Day 0 primary care consultation

These two outcomes are selected to reflect the intended impact on referral of children with severe disease (pulse oximetry and CDSA) and antimicrobial stewardship (CDSA). Severe complication outcomes are included in secondary outcomes rather than primary as, given the pre-post nature of the study, change in mortality / morbidity outcomes could be influenced by other events occurring between the baseline and post-intervention comparison phase.

Secondary outcomes:

- ξ Proportion of children with a severe complication (death or secondary hospitalisation) by Day 7
 - Secondary hospitalisation refers to any delayed hospitalisation (occurring at any point greater than 24 hours after Day 0 consultation) and any hospitalisation occurring without referral. The denominator is all enrolled children
- ξ Proportion of children admitted to hospital within 24 hours of the Day 0 primary care consultation and as a result of a referral
 - This is used as a proxy for 'appropriate referral' of children, as those with severe disease should generally be admitted to hospital. The denominator for this outcome is also all children enrolled in the study, rather than only referred children. This is because the proportion of referred children that are admitted may be high in routine care, in the context of an inappropriately low referral rate. The aim of the intervention is therefore to increase the overall referral rate of children with severe disease. Hospital admission is chosen as the proxy of severe disease rather than using primary care classification of severe disease, as there are inadequacies in the classification of severe disease in routine practice
- ξ Proportion of children who completed referral as reported at day 7 follow-up
- ξ Proportion of children cured (defined as caregiver reported recovery from illness) at Day 7 follow-up

Sub-groups for analysis of primary and secondary outcomes:

- ξ Age (under 2 months, 2 – 12 months, 13 – 59 months)
- ξ Sex
- ξ Presentation with cough / difficulty breathing

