6.1.1 General definitions

Day 7 assessment

Day 7 assessment refers to information reported by the caregiver after Day 0 and recorded in Day 7 form. Data collected as part of unscheduled visits are also integrated in these forms. If multiple successful follow-up assessments for the same child are recorded within the Day7 database, the most recent follow-up assessment will be used. To limit potential recall bias, assessments conducted far beyond the expected follow-up time will be dropped, i.e. 30 days from Day 0.

Death

A child will be considered deceased if, from Day 7 assessment, his/her status at the time of follow-up is “deceased”. In case of implausible death date (i.e. prior to enrolment date), death will be assumed to be within 7 days of Day0.

Hospitalisation

A child will be considered hospitalised if, from Day 7 assessment, he/she went to a hospital, was admitted overnight or if his/her status at the time of follow-up is “hospitalised”. In case of implausible hospitalisation date (i.e. prior to enrolment date), hospitalisation will be assumed to be within 7 days but after 24hrs of Day0.

Hospitalisation within 24hrs of Day0

For the purpose of primary analysis, a child will be considered admitted to hospital within 24hrs of Day0 consultation if the date of hospitalisation is the same as Day0 date or is one day after Day0 date.

Referral

A child will be considered to be referred (either to a hospital or to an inpatient part of a larger primary healthcare facility) if, at Day0, the research assistant confirms that an urgent referral advice was recorded for the child. If urgency is unknown, referral will be assumed to be urgent.

Antibiotics

Antibiotics will be defined in accordance with the WHO antibiotic point prevalence survey (PPS) methodology [4, 5, 6] and therefore only antibacterials for systemic use will be taken into account.

SpO2 values

SpO₂ should be recorded during the Day0. For the outcomes, the following measures will be taken for spurious and missing SpO₂ values:

- If SpO₂ value is not available, the child will be assumed normoxaemic
- If $70 \leq \text{SpO}_2 < 90\%$, the child will be assumed (with accuracy) to have severe hypoxaemia
- If $40 \leq \text{SpO}_2 < 70\%$, the child will be assumed (with low accuracy) to have severe hypoxaemia
- If $\text{SpO}_2 < 40\%$, the value will be considered spurious (e.g. due to incorrect dataentry) and treated as not available, i.e. the child will be assumed normoxaemic.

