6.1.2 Health, hospitalisation and referral outcomes

6.1.2.1 Proportion of children with a severe complication by Day 7

Severe complication is defined as death or secondary hospitalisation. Secondary hospitalisation refers to any delayed hospitalisation (occurring at any point greater than 24hrs after the Day 0 consultation) and any hospitalisation occurring without a referral. Information on death and hospitalisation will be taken from Day7 follow-up assessment.

Death will be counted in the numerator if death date is within 7 days of Day0 (7th day included). Hospitalisation will be counted in the numerator if the child was not referred at Day0 or hospital admission date is within 7 days of Day0 (7th day included) but after 24hrs of Day0.

The denominator will be all children recruited. Children for whom no death and hospitalisation data are available or withdrew prematurely from the study will be assumed to be alive and not hospitalised by Day7.

6.1.2.2 Proportion of children admitted to hospital within 24 hours of Day 0 consultation and as a result of a referral

Information on hospitalisation will be taken from Day7 follow-up assessment.

Hospitalisation will be counted in the numerator only if the child received a referral advice (as per definition above) at Day0 and hospital admission date is within the end of the following day. The denominator will be all children recruited.

Additionally, the proportion will be calculated and reported using only children who were referred as denominator.

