6.1.5 Hypoxaemia-related outcomes – in post-intervention only

6.1.5.1 Proportion of children with severe, moderate and mild hypoxaemia, adjusted for sites at high altitude

Hypoxaemic children will be summarised disaggregated by groups based on the following SpO₂ values ranges: SpO₂ < 90%, 90% ≤ SpO₂ < 92% and 92% ≤ SpO₂ < 94%. All children recruited will be in the denominator.

All facilities in Senegal are in low altitude area and therefore no adjustment is required. Only few facilities from one district in Kenya were above 2000m but cut-off for referral was not adjusted and therefore no adjustment will be applied.

6.1.5.2 Proportion of children with hypoxaemia (according to differing cut-offs) with severe complication

Children with severe complication will be summarized disaggregated by groups based on the following SpO₂ values ranges: SpO₂ < 90%, 90% ≤ SpO₂ < 92% and 92% ≤ SpO₂ < 94%, spurious values and missing values. Each SpO₂ group will be the denominator of each proportion.

6.1.5.3 Proportion of children with severe hypoxaemia not meeting any other clinical criteria for severe disease

Children with severe hypoxaemia (according to country's specific cut-off) not meeting any other clinical criteria for severe disease will be counted in the numerator. All children recruited will be in the denominator.

Severe disease will be defined in a separate document.

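### Severe complication by SpO2 band leaves out prompt admissions after referral, so the table tends to understate risk below the SpO2 referral cut-off relative to above it

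*Protocol*

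**What the plan says.** - **Objective.** Protocol section 4 sets out to "understand the association of different degrees of hypoxaemia with adverse outcomes".
- **Outcome.** The Protocol summary lists "Proportion of children with hypoxaemia (according to differing cut-offs) with severe complication" among the important secondary outcomes. Protocol 6.4.1 and SAP 3.1.4 place it lower, under other outcomes of interest.
- **Table.** SAP 6.1.5.2: "Children with severe complication will be summarized disaggregated by groups based on the following" SpO2 ranges, namely <90%, 90 to <92% and 92 to <94%, plus spurious and missing values. Each group is its own denominator. SAP 6.1.5 is restricted to the post-intervention period.
- **Event.** SAP 6.1.2.1: "Severe complication is defined as death or secondary hospitalisation". Protocol 6.4.1 defines secondary hospitalisation as "any delayed hospitalisation (occurring at any point greater than 24 hours after Day 0 consultation) and any hospitalisation occurring without referral". The SAP's counting rule is "Hospitalisation will be counted in the numerator if the child was not referred at Day0", or if admission came after 24 hours and by Day 7. SAP 6.1.1 treats an admission as within 24 hours "if the date of hospitalisation is the same as Day0 date or is one day after Day0 date".
- **Referral trigger.** Protocol 6.3 advises referral below 90% in Kenya and below 92% "in Senegal in line with national guidance".
- **Reporting level.** SAP section 6 reports analyses overall and by country.

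**The concern.** Taken together, these rules score a surviving child who is referred and admitted on Day 0 or Day 1 as free of severe complication. A child who is not referred and is admitted on the same day is scored as an event. Because low SpO2 prompts referral, the variable that defines the rows also influences whether an admission counts in the numerator.

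Leaving out prompt referred admissions makes sense in the pre-post comparison. There, Protocol 6.4.1 uses them as a separate proxy for appropriate referral and treats admission as a marker of severe disease. The difficulty comes from reusing the same composite to describe risk by degree of hypoxaemia. What is at stake is how well this table serves the section 4 objective. The listed bands stop at 94%, so the comparisons it invites are between neighbouring bands, where the referral cut-offs lie.

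**Working it through.** The documents give no expected risk, referral or admission timing by SpO2 band, so there is no plan figure to reproduce for this outcome. All inputs below are assumptions; only the counting rule comes from the documents.

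**1. Formula.** For one band, let d = death by Day 7, h = admission by Day 7 among survivors, r = probability of Day 0 referral, and c = probability that a referred child's admission falls on Day 0 or Day 1. Take h as unaffected by referral.

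- Every admission counted: d + (1 − d)h
- Planned event: d + (1 − d)h(1 − rc)

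For the admission part, the risk ratio across the cut-off is multiplied by (1 − rc below)/(1 − rc above). With rc above = 0.10 × 0.8 = 0.08, the factor is 0.87, 0.65, 0.43 and 0.22 for rc below = 0.2, 0.4, 0.6 and 0.8.

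**2. Worked example.** Below the cut-off d = 2%, h = 18%; above it d = 0.5%, h = 8%, r = 10%; c = 0.8.

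- Every admission counted: 0.02 + 0.98 × 0.18 = 19.6%, against 0.005 + 0.995 × 0.08 = 8.5%; ratio 2.32.
- Planned event above the cut-off: 0.005 + 0.0796 × 0.92 = 7.8%.

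| Referral below cut-off | Planned event below | Ratio to 7.8% |
|---|---|---|
| 50% | 0.02 + 0.1764 × 0.60 = 12.6% | 1.61 |
| 70% | 0.02 + 0.1764 × 0.44 = 9.8% | 1.25 |
| 90% | 0.02 + 0.1764 × 0.28 = 6.9% | 0.89 |

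**3. When the order swaps.** With rc above = 0.08, the planned risk below the cut-off falls under that above it once rc below exceeds:

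| d below / above | h below / above | True ratio | rc needed |
|---|---|---|---|
| 2% / 1% | 15% / 10% | 1.53 | 0.45 |
| 2% / 0.5% | 18% / 8% | 2.32 | 0.67 |
| 3% / 1% | 30% / 10% | 2.94 | 0.76 |
| 5% / 1% | 30% / 10% | 3.07 | 0.82 |
| 2% / 0.5% | 28% / 8% | 3.48 | 0.79 |

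At 30% or 50% referral, with c from 0.6 to 0.9, none of these scenarios swapped. The closest was a true ratio of 1.53 shown as 1.01 (50% referral, c = 0.9). With no true gradient at all (d = 1%, h = 15% on both sides), rc of 0.50 below and 0.08 above gives 8.4% against 14.7%.

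**4. The 90 to <92% band.** It lies above the referral cut-off in Kenya and below it in Senegal. Ignore deaths, take a 20% admission risk in both countries and c = 0.8:

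- Kenya, 10% referred: 0.20 × (1 − 0.08) = 18.4%.
- Senegal, 80% referred: 0.20 × (1 − 0.64) = 7.2%; with 50% referred, 0.20 × (1 − 0.40) = 12.0%.

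Identical children thus differ by 18.4/7.2 = 2.6-fold, or 18.4/12.0 = 1.5-fold. A pooled figure depends on the country mix.

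**5. Whether another planned output fills the gap.** SAP 6.2.4 only moves the boundary between primary and secondary hospitalisation. The same-day version brings back next-day admissions, the 3- and 7-day versions drop more referred admissions, and none counts all admissions. SAP 6.1.5.4 gives hypoxaemic children referred, and referred and admitted, by country cut-off but not by band. No planned table gives deaths alone, or all admissions, by band.

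**The case against.** The outcome is descriptive and low-ranked in the Protocol body and the SAP, and by-country reporting is already planned. Severe complication also has a coherent meaning: death, or an admission that was late or came without referral, with prompt referred admission as the intended result. Counting any admission has the opposite circularity, since a low reading prompts referral and referral can prompt admission. Deaths count whatever the referral status, so the distortion shrinks where mortality is high. All of this stands. It argues for adding columns, not for replacing the event.

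A reader might infer that the table will reverse the relation between hypoxaemia and outcome in both countries. The documents do not support that. Take admissions alone, with true risks of 40%, 20% and 10% in the three bands, c = 0.8, and referral of 80% below the cut-off, 10% in Kenya's middle band and 5% in the top band. Kenya then shows 14.4%, 18.4% and 9.6%, and Senegal 14.4%, 7.2% and 9.6%. One neighbouring pair swaps in each country, and in Senegal <90% remains highest. At 50% referral below the cut-off, with c from 0.6 to 0.9, the lowest band is 22–28% against about 18% for Kenya's middle band, and Senegal's middle band is 11–14% against just under 10% above it, so nothing swaps. Nothing in the documents supports 80%. The figures in Protocol 3.2 come from external studies of existing practice: 38% of severely ill children referred in one, and 41% of those with severe or very severe pneumonia not referred in another.

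A reader might also infer that the threshold costing in Protocol 7.3.4 is undermined. It is not: that costing uses the extra proportion of children who would meet referral criteria. The remark in Protocol 3.1 that the cut-off needs more validation is background on ruling out severe disease, not a task set for this table.

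**Conclusion.** The point holds as a weakness of one descriptive table. By the plan's own definitions, the measured gradient across the referral cut-off is weakened whenever the cut-off raises prompt referred admissions, and more so the better providers follow the advice. In the assumed example the ratio falls from 2.32 to 1.61 at 50% referral and to 0.89 at 90%. A swap of neighbouring bands needs high referral with prompt admission, or a modest true gradient; general reversal is not established. These sizes rest on assumed risks, referral and timing, and on admission risk not depending on referral. The pooled 90 to <92% figure mixes two referral regimes. The pre-post use of severe complication, the primary outcomes and the sample size are unaffected.

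**What to change.** In SAP 6.1.5.2, keep severe complication as planned and add for each SpO2 band:

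- death by Day 7;
- death or any hospital admission by Day 7, whatever the referral status or timing;
- the proportion referred at Day 0.

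State that the 90 to <92% band is read by country and that its pooled figure is not interpreted.

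The cost is a few extra columns from Day 0 and Day 7 data already collected. The downside is that any admission includes some admissions prompted by the low reading itself, so the SAP should say that the columns are to be read side by side.
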